1 STUDY SYNOPSIS

Sponsor / Sponsor-Investigator	Name(s) and contact details of Sponsor / Sponsor-Investigator
Study Title	Full protocol title
Short Title / Study ID	Abbreviated protocol title or, if applicable, study ID, e.g. study number
Protocol Version and Date	Version x (dated DD/MM/YYYY)
Study Registration	Name of study registry, registration number (if not yet registered, name the intended registry)
Study Category and Rationale	Risk category and rationale
Background and Rationale	Background of the study and rationale
Risk / Benefit Assessment	Risk / benefit assessment
Objective(s)	Primary objective(s) and, if applicable, secondary including safety objective(s)
Endpoint(s)	Primary endpoint(s) and, if applicable, secondary including safety endpoint(s)
Study Design	Design attributes (e.g. confirmatory, non-randomised / randomised, open / single-blinded / one-arm / two-arm, cross-over/controlled)
Statistical Considerations	Description of the main elements of the statistical methodology to be used in the study including an explanation to sample size
Inclusion- / Exclusion Criteria	key inclusion and exclusion criteria and, if applicable, rationale for including vulnerable participants
Number of Participants with Rationale	Number of participants in the entire study, provide the total number as well as the number for each treatment group. Briefly explain the rationale for the number of participants.
Study Intervention	Description of the study intervention
Control Intervention	If applicable, description of the control group
Study procedures	Description of the overall study procedures
Study Duration and Schedule	Estimated duration for the main investigational plan, i.e. from start of screening of first participant to last participant last visit and finishing the study Planned MM/YYYY of First-Participant-In Planned MM/YYYY of Last-Participant-Out
Investigator(s)	Name(s) and contact details of Investigator(s)
Study Center(s)	Name(s) and address of Study Center(s) If multicenter study, number of centers to be involved If multinational study, countries to be involved
Data privacy	Explain how the privacy of data is guaranteed. Mention coding and confidentiality while handling data and if applicable biological material.
Ethical consideration	Explain the scientific value of the study, justify the methodology give a statement to the risks and the benefit. Explain if you include vulnerable populations.
GCP Statement	This study will be conducted in compliance with the protocol, the current version of the Declaration of Helsinki, the ICH-GCP, the HRA as well as other locally relevant legal and regulatory requirements. A clinical trial covered by ClinO Chapter 4 may be conducted in accordance with other rules than ICH-GCP guidelines, provided that such rules are recognised in the specialty in question and the protection of participants and data quality and security are guaranteed (ClinO Art. 5, Abs 2). If the clinical trial is not conducted according to ICH-GCP guidelines, the paragraph above must be adapted accordingly.

2 BACKGROUND AND RATIONALE

Low back pain (LBP) constitutes a global public health concern, affecting an estimated 619 million individuals across all age groups (Collaborators, 2023; Hartvigsen et al., 2018; Hoy et al., 2012). Projections, based on trends in population growth and aging, suggest that by the year 2050, there will be a further increase of 36.4%, resulting in a total of 843 million individuals worldwide affected by LBP (Collaborators, 2023). In 2020, low back pain accounted for a 7.7% of all years lived with disability (YLD) globally, establishing it as the primary cause of the world's disability burden, accompanied with substantial associated costs of care (Collaborators, 2023). Approximately one third of individuals experience a recurrence of low back pain within one year after recovering from a prior episode (da Silva et al., 2017). For most individuals presenting with low back pain, to pinpointing a specific cause proves challenging. Consequently, these individuals are classified as having non-specific low back pain (Maher et al., 2017). While there are numerous potential causes of LBP, it has been suggested that these often relate to weakness of the muscles responsible for extending the lumbar spine (lumbar erector spinae and multifidus) (Steele et al., 2014).

Isolated lumbar extension (ILEX) training utilizing resistance machines has demonstrated superior effectiveness in strengthening the lumbar extensors compared to alternative methods such as bench and roman chair trunks extensions, free weight exercises, or floor and stability ball exercises (Steele et al., 2015b). Furthermore, ILEX resistance training has shown efficacy in reducing pain and improving disability associated with LBP (Steele et al., 2015a). What sets ILEX resistance machines apart is their unique ability to isolate the lumbar muscles to be primarily responsible for the work performed by stabilizing the pelvis through specially designed restraints. Previous studies have documented the necessity of pelvic stabilization in order to optimal increases in low back strength by eliminating the contribution of gluteal and hamstring muscles (Graves et al., 1994; Smith et al., 2011). Moreover, it has been established that a semi-sitting position is the most effective to reduce the activation of the hip extensor muscle (da Silva et al., 2009).

Exercise training is a powerful stimulus for physiological adaptations and a crucial aspect of maintaining good health (Egan & Zierath, 2013). Resistance exercises are particularly effective in enhancing skeletal muscle development, growth, and function (Egan & Zierath, 2013). However, factors such as limited physical capabilities and poor health status can prevent individuals from meeting the recommended level of exercise (Fennel et al., 2022). Recently, there has been an increasing interest in the potential of heat as adaptive aid to promote hypertrophy in resistance training. There is some evidence that heat stress alone (Ihsan et al., 2020; Rodrigues et al., 2020) and in combination with resistance exercise (Goto et al., 2007; Nakamura et al., 2019; Yoon et al., 2017) can increase hypertrophy and associated muscle strength. Heat shock proteins (HSPs), expressed in response to stimuli including heat stress and exercise, play a critical role in protecting from muscular atrophy or confer hypertrophic benefits (Fennel et al., 2022). The exact mechanisms by which HSPs might associate with or influence relevant signalling responses in skeletal muscle are not fully elucidated (Fennel et al., 2022). It has been known that expression of HSPs in skeletal muscle increases when the muscle temperature is increased over 40°C (Oishi et al. 2002 (Oishi et al., 2002; Selsby & Dodd, 2005). To date, four studies have investigated the impact of repeated heat stress in direct combination with resistance training over a period of several weeks (Goto et al., 2007; Nakamura et al., 2019; Stadnyk et al., 2018; Yoon et al., 2017). Three studies found a beneficial effect (Goto et al., 2007; Nakamura et al., 2019; Yoon et al., 2017), whilst one study reported no evident advantages (Stadnyk et al., 2018). Training protocols, involved muscle groups, as well as type and duration of heat applications varied in the four studies. Nakamura and colleagues concluded that incorporating heat stress prior to resistance training, rather than afterwards, may be crucial for enhancing muscle mass and increasing strength (Nakamura et al., 2019). To the best of our knowledge, no studies have been published to investigate the effect of heat stress and resistance training on the back extensor muscle.

Different methods can be used to heat the whole body or specific body areas. Shortwave or microwave electromagnetic diathermy is a heating modality that uses a radiofrequency electromagnetic field to increase the temperature in deeper structures, such as muscles, without an excessive increase of skin temperature to uncomfortable levels (Guy et al., 1974).

Microwave diathermy has shown to increase muscle temperature by ~3-7°C depending on the time of application and power of the instrument (Castellani et al., 2016; Draper et al., 1999; Nosaka et al., 2007; Nosaka et al., 2004).

The aim of this study is to investigate strength gains of the back extensor after 6 weeks of resistance training on an ILEX machine in combination with microwave diathermy.

3 STUDY OBJECTIVES AND DESIGN

3.1 Hypothesis and primary objective

The main aim of this study is to investigate the effect of back extensor strength after 6 weeks of ILEX training and diathermy therapy.

- H_0 : 6 weeks of resistance training on the ILEX machine does not improve lumbar extensor muscle strength.
- H_1 : 6 weeks of resistance training on the ILEX machine improves the strength of the lumbar extensor muscle.
- H_0 : There is no difference in the improvement in lumbar extensor muscle strength between those who receive a microwave diathermy treatment before each resistance training session and those in the sham group.
- H_1 : Individuals who receive a microwave diathermy treatment prior to each resistance training session improve their lumbar extensor muscle strength more than those in the sham group.

Secondary objectives are to examine the development of M. erector spinae thickness, isometric back extension endurance, and lumbar extensor flexibility after 6 weeks of resistance training and diathermy therapy.

- H_0 : 6 weeks of resistance training on the ILEX machine does not enhance the thickness of the M. erector spinae.
- H_1 : 6 weeks of resistance training on the ILEX machine enhances the thickness of the M. erector spinae.
- H_0 : There is no difference in the increase of the thickness of the M. erector spinae between those who receive a microwave diathermy treatment before each resistance training session and those in the sham group.
- H_1 : Individuals who receive a microwave diathermy treatment prior to each resistance training session enhance the thickness of the M. erector spinae more than those in the sham group.
- H_0 : 6 weeks of resistance training on the ILEX machine does not improve isometric back extension strength endurance.

- H_1 : 6 weeks of resistance training on the ILEX machine improves isometric back extension strength endurance.
- H_0 : There is no difference in the improvement of the isometric back extension strength endurance between those who receive a microwave diathermy treatment before each resistance training session and those in the sham group.
- H_1 : Individuals who receive a microwave diathermy treatment prior to each resistance training session improve the isometric back extension strength endurance more than those in the sham group.
- H_0 : 6 weeks of resistance training on the ILEX machine does not increase lumbar ROM.
- H_1 : 6 weeks of resistance training on the ILEX machine increases lumbar ROM.
- H_0 : There is no difference in the increase of the lumbar ROM between those who receive a microwave diathermy treatment before each resistance training session and those in the sham group.
- H_1 : Individuals who receive a microwave diathermy treatment prior to each resistance training session increase of the lumbar ROM more than those in the sham group.

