3.3 Study design

This is a monocentric clinical trial with minimal risks and burden of the risk class A (KlinV, Art. 20). A block randomization with covariates (i.e. sex) is used. The preheating is done as a single blinded randomized controlled trial (RCT) with the sham group receiving a 10-minute diathermy treatment with the Tecar device turned off and not sending radiofrequency before each exercise session. The intervention group undergoes a 10-minute treatment with the Tecar device to induce 448kHz capacitive monopolar radiofrequency and facilitate warming up of deep tissues. In order to be able to carry out a single-blind situation as far as possible, the test subjects are not told that the therapy causes heat of the deep tissue and that this is the factor being investigated. Instead, we speak of high-frequency Tecar therapy and its known use to promote tissue healing processes.

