3.4. Study intervention

We recruit a cohort of 14 healthy persons, both men and women, who have not trained their back extensors in isolation in the last 12 months. During a 6-week program consisting of a total of 12 sessions, the participants receive a diathermy treatment with the CE-certified device Tecar (T-Plus, Wintecare SA, Chiasso, Switzerland) and carry out a back extensor resistance training on the CE-certified ILEX machine Myosom (Heftec GmbH, Oberurnen, Switzerland).

Participants are randomly assigned to either the sham group, which receive a 10-minute treatment with the diathermy device turned off and not sending radiofrequency before each exercise session, or the intervention group, which undergo a 10-minute diathermy treatment to induce 448kHz capacitive monopolar radiofrequency and facilitate warming up of deep tissues. After all treatments participants are asked to rate their thermal sensation and comfort.

After the 10-minute diathermy treatment, the participants are seated in the ILEX machine in a semi-seated position with the feet placed on a footrest. The lumbar back is leaning against a round restraint that is free to rotate on its axis, the thoracal back against a squared restraint, hosting the load cells measuring torques produced by the left and right side separately. The machine incorporates a counterweighting procedure to counterbalance the effect of gravity acting on the upper body. Restraining belts are secured around the pelvis and around both shoulders. Over the anterior part of the upper thigh a restraint pad is positioned. All restraints

are tightened until a pressure but not pain occurs. These restraints prevent unwanted vertical movement of the pelvis or thighs.

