Training will take place twice a week, beginning with a dynamic warm-up of the lumbar extensor for 120s, followed by three sets of resistance training lasting 120s, 120s, and 150s respectively, and concluding with a final set of dynamic recovery lasting 60s. 30-second recovery will be provided between every set. A low load will be used for the warm-up and recovery. The initial load is based on the maximum isometric force and subsequently increased until volitional fatigue. Repetitions will be executed by taking three seconds from complete flexion to complete extension, ensuring standardization at 20 repetitions per minute. A metronome with 40 beats per minute will provide audible feedback. The ILEX machine emits an audible signal upon completion of each phase of the repetition to guarantee a complete range of motion (ROM) is achieved. Subsequent to every training session, participants will be requested to provide their effort (RPE-E) and discomfort (RPE-D) values.

Baseline (BL) measurements are conducted before the initiation of training, and two follow-up measurements (F/U 1 and F/U 2) carried out after the sixth and twelfth session, with a minimum break of 48 hours after the last training session to ensure proper recovery and to prevent inaccuracies in muscle thickness measurement arising due to acute edema. At BL, participants need to give written informed consent and be familiarized with the ILEX machine and Category-Ratio-Scale (CR10) for the assessment of perceived effort and discomfort as well as a 9-point Likert scale for thermal sensation and 5-point scale for comfort. BL assessment include epidemiological data such as age, sex, height, and weight. Physical activity is assessed using the self-administered short German version of the International Physical Activity Questionnaire (IPAQ) with a "last 7 d recall" (IPAQ Research Committee, 2005) at BL, F/U1 and F/U2. At all three measurements (BL, F/U 1, F/U 2), the lumbar extensor musculature thickness (M. erector spinae), the maximum ROM, the maximum voluntary isometric contraction, the lower back flexibility, and the isometric back extension endurance are measured. Skin temperature is measured using an infrared thermal imaging (FLIR A615 series, Emitec Industrial, Rotkreuz, Switzerland) after the first and final diathermy treatment.

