appendix 1.

12 sessions of back extensor resistance training on the ILEX machine take place over a 6-week period (twice a week). Before each exercise, a diathermy treatment is taking place. Before, after 6 sessions and after completion of the 12 sessions, tests are conducted on separate days.

On intervention days, the participants enter the RES laboratory in Landquart wearing sports clothing. First, they lay on an examination table in a prone position receiving a treatment with the diathermy device for 10 minutes from a trained examiner. The intervention group is treated with the diathermy device inducing 448kHz capacitive monopolar radiofrequency, warming up the deep tissues. The sham group receives a massage with the diathermy device without radiofrequency. Directly after the first and last diathermy treatment, a picture will be taken with an infrared camera (FLIR A600 series, Emitec Industrial, Rotkreuz, Switzerland). Then, participants translocate to the ILEX machine and are seated according to their individual settings. The training session lasts 12 minutes. Participants begin the training session with a dynamic warm-up of the lumbar extensor for 120s, followed by three sets of resistance training lasting 120s, 120s, and 150s respectively, and concluding with a final set of dynamic recovery lasting 60s. Between each set, a 30-second recovery is provided. Repetitions will be executed by taking three seconds from complete flexion to complete extension, ensuring standardization at 20 repetitions per minute. A metronome with 40 beats per minute will provide audible feedback. The ILEX machine emits an audible signal upon completion of each phase of the repetition to guarantee a complete ROM is achieved. A low load is used for the warm-up and recovery. For the three training sets, the initial load is based on the maximal isometric force and subsequently increased until volitional fatigue. Immediately subsequent to each training session, participants will be requested to provide their effort (RPE-E) and discomfort (RPE-D) values. Immediately after the first and final diathermy treatment before dislocating to the ILEX machine, participants skin temperature is measured while laying prone on the examination table making an imaging with the FLIR camera.

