On the examination days (BL, F/U1 and F/U2), the participants enter the RES laboratory in Landquart wearing sports clothing. At baseline, participants are asked to sign an informed consent form and are screened for inclusion and exclusion criteria. Participants are then asked for their age and sex, height is measured using a stadiometer (GPM Stadiometer, Zurich, Switzerland), and weight and lower body fat percentage are measured using a scale (TANITA-TBF 611 scale, Tokyo, Japan). At all three measurements (BL, F/U1 and F/U2) participants are asked to complete the IPAQ to assess physical activity. Next participants are placed on the examination table in a prone position for an ultrasound scan to measure the thickness of the M. erector spinae on the right side. The probe head is coated with coupling gel and applied perpendicular to the muscle on the right side without pressure to not compress the dermal surface. The images are saved, and the distance is measured later. Participants are then familiarised with the ILEX machine and positioned for individual adjustments. After a warmup for 120s with a low load and a short break, participants are asked to move dynamically into full flexion and full extension over the full ROM for three times. The test is repeated a second time. After a 2-minutes break, participants are asked to slowly move backwards to maximal tension and repeat the isometric force test after 2-minutes break. Next, the participant is seated in front of the sit-and-reach test box keeping the knees fully extended and the feet dorsiflexed against the foot-support. The participant is moving actively, slowly forward, bringing the body to the pain-free limit. The participant's hands move along the scale on the block until the movement is terminated because the participant can go no farther. The final position is held with an isometric contraction for 2 seconds, and the distance is read on the scale. After a 2-minutes break, the test is repeated. The rating scales for perceived effort, discomfort and thermal sensation are then presented for familiarization. Finally, the isometric back extension endurance is measured through the Biering-Sørrensen test. The participant is lying prone on an examination table with the upper border of the iliac crests in line with the edge of the table. The lower body is secured to the table by three straps around the pelvis, knees, and ankles. With the arms folded across the chest, the participant is asked to hold the upper body isometrically in a horizontal position. A stopwatch is used to measure the time the participant can keep the unsupported upper body in contact with a horizontal object. The examination takes about 1 hour.

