5 STATISTICS AND METHODOLOGY

5.1. Statistical analysis plan and sample size calculation

A priori sample size calculation was performed using G*power (Version 3.1, Franz Faul, Germany) to determine participants numbers (n) ($\alpha = 0.05$; effect size = 0.46; test family = F test, and statistical test = analysis of variance (ANOVA) repeated measures, within-between interaction; number of groups = 2; number of measurements = 3; power = 0.8) and revealed n = 10 participants. The effect size was estimated based on previous research with a comparable ILEX device in healthy volunteers (Fisher et al., 2018).

Assumption of normality will be verified using the Shapiro-Wilk test. Mauchly's test will indicate the violation of the assumption of sphericity. Normally distributed data will be analysed applying ANOVA repeated measures with within-between interactions to compare the means of each variable over the three repeated observations (within) and between the intervention and sham group (between). Not normally distributed data will be examined using non-parametric statistics (Friedman's two-way ANOVA). Post hoc Bonferroni test correction will be applied. Probability values $p < 0.05$ will be considered statistically significant.

Men and women are included in this study and will be part of the randomization process. The planned sample size of this study does not allow for gender-specific analysis. A gender difference analysis will have to be part of a future study.

Analyses will be performed using RStudio Team (2023) (RStudio: Integrated Development Environment for R. Boston, MA) and IBM SPSS Statistics (Version 27, IBM Corp., Armonk, NY, USA).

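### A primary hypothesis credits strength gain to training, but no arm goes untrained; the non-normal fallback also leaves diathermy versus sham without a test

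*Combined protocol and SAP*

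**What the plan says.** - **Hypotheses (section 3.1).** Two pairs of null and alternative hypotheses sit under the primary objective. The first alternative is that "6 weeks of resistance training on the ILEX machine improves the strength of the lumbar extensor muscle"; it names no comparator. The second is that diathermy before training improves strength more than sham. One main aim covers both, and no order or alpha split is given. The secondary objectives repeat the pairing for muscle thickness, endurance and ROM.
- **Design (sections 3.3, 3.4, 4.3).** Section 3.3 applies the term RCT to the preheating only. All 14 participants receive a diathermy or sham treatment and "carry out a back extensor resistance training on the CE-certified ILEX machine Myosom", for 12 sessions. No untrained arm, waiting period or repeated baseline is described. In the sham arm, "The sham group receives a massage with the diathermy device without radiofrequency".
- **Measurement (sections 3.2, 4.3).** Force is tested on the machine used for training, at baseline and after 6 and 12 sessions. On examination days, "Participants are then familiarised with the ILEX machine and positioned for individual adjustments"; a warm-up, two rounds of ROM movements and two force trials follow.
- **Analysis (section 5.1).** Normal data are analysed by "ANOVA repeated measures with within-between interactions to compare the means of each variable over the three repeated observations" and between the two groups. Non-normal data go to Friedman's test. The sample size is calculated for the within-between interaction. No test is assigned to the training hypothesis; the natural reading is the time term.

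**The concern.** The training hypothesis is worded as cause and effect, yet the trial randomises nothing that bears on it. The within-subject time term measures everything that changes between baseline and follow-up, and training is only one part of that. Because the two primary hypotheses are unranked, a significant time term could be reported as a positive primary result and as a training effect even if diathermy shows nothing. The design cannot support that statement.

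The fallback raises a separate problem that exists however the hypotheses are ranked. If the data fail the Shapiro-Wilk check, the plan leaves a test of change over time and none of diathermy versus sham, which is the comparison the trial was randomised and sized to make.

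**Working it through.** **1. The plan's own figure.** For the repeated-measures interaction, λ = f²·N·m/(1−ρ), with df 2 and 2(N−2). The plan gives f = 0.46, m = 3, α = 0.05 and power 0.8. It does not state ρ or sphericity; ρ = 0.5, sphericity and equal groups are assumed here.
- N = 8: λ = 0.2116 × 8 × 3 / 0.5 = 10.16, power 0.709.
- N = 10: λ = 12.70, power 0.833. The stated n = 10 is reproduced.
- N = 14: λ = 17.77, power 0.952.

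This calculation concerns diathermy versus sham. It says nothing about whether training causes a gain.

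**2. What each contrast contains.**

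| Contrast | Contains | Randomised? |
|---|---|---|
| Difference between arms in change | Effect of radiofrequency on versus off | Yes |
| Change in the sham arm | Training, retest and device practice, device massage, passage of time | No |
| Change pooled over arms | All of these, plus any heat effect | No |

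No contrast isolates training.

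**3. How easily the time test could mislead (illustration).** Assumptions, none from the documents: 7 per arm, compound symmetry, no true training gain, and a common practice gain g in units of the SD of change. With G = g√2, λ = 14 × the sum of squared deviations of the three time means; df are 2 and 24.
- Step pattern (0, G, G): the sum is 2G²/3 = 4g²/3, so λ = 18.67g².
- Linear pattern (0, G/2, G): the sum is G²/2 = g², so λ = 14g².

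| g | λ step | P(significant), step | λ linear | P(significant), linear |
|---|---|---|---|---|
| 0.3 | 1.68 | 0.177 | 1.26 | 0.143 |
| 0.5 | 4.67 | 0.426 | 3.50 | 0.330 |
| 0.8 | 11.95 | 0.835 | 8.96 | 0.711 |

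**4. The fallback.** Friedman's test ranks the three visits within each participant and asks whether the ranks differ between visits. Arm does not enter the statistic, so it has no group-by-time term whether it is run pooled or per arm. Section 5.1 names no other non-parametric test.

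**5. Power of a between-arm replacement.** For a between-arm difference D in SD of change (step pattern, 7 v 7), λ = 14D²/3 for the ANOVA interaction. Section 3.3 specifies block randomisation with sex as covariate and gives no block size, so two block layouts were simulated for a permutation test of the group-by-time sum of squares, re-allocating labels within blocks.

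| D | ANOVA interaction | Blocks of 4, 4, 4, 2 | Blocks of 2 |
|---|---|---|---|
| 1.0 | 43% | about 38% | about 33% |
| 1.53 | 80% | about 74% | about 67% |
| 1.95 | 95% | about 92% | about 88% |

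Repeat simulation gave permutation figures up to 3 points higher. D = 1.95 corresponds to the planned f = 0.46, since √(17.77 × 3/14) = 1.95.

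**The case against.** The strongest reply is that this is mostly wording. The aim closing section 2 and the endpoint text in section 3.2 are phrased as change over time, section 3.3 keeps the RCT label for the preheating, the sample size points to the interaction, and no section commits to publishing a causal training claim. Sections 2 and 4.3 also cite earlier evidence that such training works, so a true gain is plausible. All of this is fair, and it is why the remedy is a change of text. But a sample size calculation only hints at priority, section 3.1 lists the training hypothesis first, and earlier evidence does not let this trial attribute its own gain.

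The examination-day familiarisation, warm-up and repeated trials reduce first-exposure learning. They do not remove the effect of 12 further sessions on the test device. The IPAQ records other activity but cannot correct for retest.

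Two stronger readings are tempting. A reader might infer that practice undermines every training hypothesis alike. It does not: thickness is read from saved ultrasound images after at least 48 hours' rest and needs no skill from the participant, so practice matters mainly for ILEX force and ROM. What all these hypotheses share is the lack of an untrained control. A reader might also take a significant Friedman result under a common gain as a false positive for diathermy. It would be a finding about time and say nothing about the arms.

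It is also true that the interaction is a non-directional test over three visits, while the hypothesis is directional and concerns six weeks. That is a feature of the plan's own test and a separate matter.

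**Conclusion.** The point holds as one of attribution and ranking. The plan can estimate change from baseline but cannot credit it to training, and it lets that change count as a primary result. This follows from the design and needs no assumed numbers. The rates of 14–18%, 33–43% and 71–84% only show that the time test could be significant with no training effect; they rest on assumed practice gains, 7 per arm, compound symmetry and two time patterns.

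The missing between-arm test in the non-normal branch is a definite gap. The documents do not support the wider inference that the trial's randomised comparison is compromised: with normal data, the group-by-time interaction tests diathermy versus sham as intended. Nor do they support saying that training has no effect. The correction should be made before analysis, but it does not call the design into question.

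**What to change.** In sections 3.1 and 5.1:

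1. Name diathermy versus sham on maximal isometric force as the sole primary hypothesis, tested by the group-by-time interaction already used for the sample size.
2. For that comparison, replace the Friedman fallback with a between-arm test of change from baseline, for example a permutation test of the group-by-time statistic that re-allocates arm labels by the actual scheme (blocks and sex). State the block sizes.
3. Make the training hypotheses secondary, reword them as change from baseline during the programme, report them per arm with 95% confidence intervals, and state that they will not be claimed as causal effects of training. Describe the sham arm as training plus device massage without radiofrequency.

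**Cost.** Arms, visits and sample size do not change. The sponsor gives up a causal training claim as a primary result. Per-arm intervals are wider than pooled ones: the half-width t(0.975, n−1)/√n is 0.925 SD of change at n = 7, against 0.577 for all 14. In the non-normal branch, power is below the ANOVA's and depends on block size, as tabulated above; very small blocks cost most. The fix adds no power to the primary test.
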